This study will be the first of its kind to utilize blinding and a control while analyzing BoNT-A injections for CECS in the military health system. It will also be the first to judge whether formal gait retraining is required for the successful non-operative treatment of CECS or if BoNT-A injections is sufficient as a stand-alone treatment. The information gained from this study has the potential to revolutionize the treatment of CECS and provide guidance to physicians caring for these patients all over the world.

9.3

Objectives/Specific Aims/Research Questions:

Describe the purpose and objective(s) of the study, specific aims, and/or research questions /hypotheses

The long-term objective of this project is to simultaneously assess the effectiveness of non-surgical treatments, botulinumtoxin A (BoNT-A) injections and supervised gait retraining (SGR), in terms of pain control and ability to return to full duty among adult active duty service members suffering from lower extremity Chronic Exertional Compartment Syndrome (CECS), specifically of the anterior and/or lateral compartments.^{1,2,3}

This study will determine if successful supervised gait retraining is required for the successful non-operative treatment of anterior and/or lateral CECS or if BoNT-A injections is sufficient as a standalone treatment. Furthermore, this study will determine if BoNT-A injections plus supervised gait retraining is better.

Study Treatment Groups:

- Group 1 - Home Based Gait Retraining (HBGR) and Normal Saline (placebo)
- Group 2 - Supervised Gait Retraining (SGR) and Normal Saline (placebo)
- Group 3 - BoNT-A + HBGR
- Group 4 - BoNT-A + SGR

Objective 1: Assess and compare the treatment efficacy of the below study treatment groups.

Hypothesis 1: BoNT-A injections will prove effective as a non-surgical treatment option for CECS.

Process for Hypothesis 1: Evaluate functional improvements in Group 3 as compared to Group 1 via the subjective and objective data variables described in protocol sections 10.1 & 10.2.

Hypothesis 2: Supervised Gait Retraining will prove effective as a non-surgical treatment option for CECS.

Process for Hypothesis 2: Evaluate functional improvements in Group 2 as compared to Group 1 via the subjective and objective data variables described in protocol sections 10.1 & 10.2.

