In keeping with statistical analysis standards in randomized controlled trials, data will be analyzed using complete-case, intention-to-treat (ITT) analysis—that is, we will analyze all study subjects who received treatment assignment and for whom we obtained sufficient outcome data.

Confounding Variables:

Clinical effectiveness will be studied using a factorial randomized design. Such designs are widely recognized to yield unbiased estimates by removing confounding between treatment and outcome when sufficiently powered.

11.2 Sample Size:

We are requesting to enroll up to 620 participants (155 per treatment group) across all performance sites in order to evaluate a final sample of 480 subjects (120 per treatment group) across all performance sites. Up to 125 of these participants will be enrolled at WRNMMC. Up to 125 of these participants will be enrolled at each of the other performance sites.

11.3 Total number of subjects requested (including records and specimens):

620

11.4 If you are recruiting by study arm, please identify the arms of the study and how many subjects will be enrolled in each arm

Across all performance sites, up to 620 participants will be uniformly randomized across the four treatment groups: Up to 155 participants in Group 1 - Home Based Gait Retraining (HBGR) and Normal Saline (placebo), up to 155 participants in Group 2 - Supervised Gait Retraining (SGR) and Normal Saline (placebo), up to 155 participants in Group 3 - BoNT-A + HBGR, and up to 155 participants in Group 4 - BoNT-A + SGR.

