11.5 Please provide a justification for your sample size

Using a 2x2 factorial design and assuming success rates for passing the US Army 2-mile run test among control (saline/home based gait retraining), botulinumtoxin A (BoNT-A) injection, supervised gait retraining (SGR), and combined therapy (BoNT-A + SGR), respectively, are 15%, 80%, 50%, and 85%, we estimate that enrolling a grand total of at least 60 patients would yield 80% power to detect the effect of BoNT-A, enrolling a grand total of at least 120 patients would yield 80% power to detect the effect of SGR, and enrolling a grand total of at least 380 patients would yield 80% power to demonstrate the benefit of combined therapy (BoNT-A + SGR) vs. either therapy in isolation. If we can obtain complete data on more than 380 participants, then it will strengthen our power. We hope to have a final sample of 480 participants. Assuming roughly 20% attrition and accounting for screen failures, we are requesting to enroll up to 620 participants across all performance sites.

Power was estimated using Monte Carlo simulations assuming uniform randomization among four groups in the 2x2 factorial design, while testing for statistical significance simultaneously among the four groups of control, BoNT-A, SGR, and combined therapy using a generalized linear model. Statistical significance was indicated if the corresponding $p < 0.05$ per generalized linear model.

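### The 80% power claimed at 380 patients does not hold for combined therapy against BoNT-A alone: on the plan's own 2-mile-run rates it is about 14% (17% at 480)

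*Combined protocol and SAP*

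**What the plan says.** Section 11.5 bases the sample size on passing the Army 2-mile run. The assumed success rates for control, BoNT-A, SGR and combined therapy "respectively, are 15%, 80%, 50%, and 85" percent. From these it derives three totals, each for 80% power: 60 for the BoNT-A effect, 120 for the SGR effect, and for the combination "at least 380 patients would yield 80% power to demonstrate the benefit of combined therapy (BoNT-A + SGR) vs. either therapy in isolation". The method is Monte Carlo simulation "assuming uniform randomization among four groups in the 2x2 factorial design", and "Statistical significance was indicated if the corresponding $p < 0.05$ per generalized linear model". The link function, the sidedness and the contrast behind the 380 are not given.

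Hypothesis 3 in section 9.3 has the combination beating each treatment alone, assessed by comparing group 4 with groups 2 and 3. The same section promises an answer on the role of SGR: "This study will determine if successful supervised gait retraining is required for the successful non-operative treatment".

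Section 11.1 specifies logistic regression with three group indicators and group 1 as the reference. It describes the group 4 coefficient as the effect of group 4 against group 2 or 3.

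The plan hopes for 480 evaluable patients (120 per arm). On enrolment, 11.5 says: "Assuming roughly 20% attrition and accounting for screen failures, we are requesting to enroll up to 620 participants across all performance sites". Section 11.4 says that "up to 620 participants will be uniformly randomized across the four treatment groups".

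**The concern.** Combined therapy has to beat the stronger single therapy as well as the weaker one. On the plan's figures the stronger one, BoNT-A with home-based retraining, already succeeds in 80%, which leaves a 5-point difference to detect. A difference that small near 80% cannot be found with 80% power at 95 per arm.

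Of the three stated totals, 380 is the largest and the one that supports the 480 target; the other two effects need only 60 and 120. A reader who trusts the 80% could take a non-significant group 4 v 3 result as evidence that supervised retraining adds nothing to BoNT-A. On the plan's own assumptions that result is the expected one, even though a 5-point benefit exists.

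**Working it through.** **Inputs (section 11.5).** Rates: control 0.15, BoNT-A 0.80, SGR 0.50, combined 0.85. Equal allocation, so 380 is 95 per arm, 480 is 120 and 620 is 155. Significance at 0.05, taken as two-sided.

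**Reproducing the plan's figures.** Logistic Wald simulation with uniform randomisation gives 82% power for BoNT-A v control at 60 and 82% for SGR v control at 120. Both agree with the plan, so its general method is recoverable. The 380 figure is not.

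**Group 4 v 3, closed form.** With p̄ = (0.85 + 0.80)/2 = 0.825:

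- se0 = √(2 × 0.825 × 0.175 / n) = √(0.28875/n)
- se1 = √((0.85 × 0.15 + 0.80 × 0.20)/n) = √(0.2875/n)
- power = Φ[(0.05 − 1.96 × se0)/se1]

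At n = 95: se0 = 0.0551, se1 = 0.0550, so power = Φ[(0.05 − 0.1081)/0.0550] = Φ(−1.055) = 14.6%.

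| Total (per arm) | 4 v 3, closed form | 4 v 3, logistic simulation |
|---|---|---|
| 380 (95) | 14.6% | 14.0% |
| 480 (120) | 17.3% | 16.8% |
| 620 (155) | 21.1% | 20.8% |

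One-sided power would be 23% at 380 and 27% at 480.

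**Size needed for 80%.** n per arm = [1.96 × √0.28875 + 0.842 × √0.2875]² / 0.05² = (1.053 + 0.451)² / 0.0025, about 906. In four arms that is 4 × 906 = 3,624.

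**Group 4 v 2 (85% v 50%).** Power at 380 is above 99.9% by the closed form and by simulation. Power to beat both single therapies is therefore set by 4 v 3: 14.0% at 380 and 16.8% at 480 by simulation. The chance of a non-significant 4 v 3 result is about 86% and 83%.

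**Other readings of the 380.**

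- Group 4 v the two single-therapy arms pooled: 96%.
- Group 4 v 1: near 100%.
- 2×2 interaction, logit scale: logit 0.85 − logit 0.80 − logit 0.50 + logit 0.15 = 1.735 − 1.386 − 0 − 1.735 = −1.386. Its variance at 95 per arm is (7.843 + 6.25 + 4 + 7.843)/95 = 0.273, so se = 0.5225 and power = Φ(1.386/0.5225 − 1.96) = Φ(0.69), about 75–76%.
- 2×2 interaction, probit scale: about 81%.

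The interaction comes closest to 80%, but it is negative: the joint effect is less than additive. A significant result on it would not show that the combination beats either therapy.

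**What 480 can detect.** At 120 per arm, 92.5% v 80%: p̄ = 0.8625, se0 = 0.0445, se1 = 0.0437, power = Φ[(0.125 − 0.0871)/0.0437] = Φ(0.87), about 81%. At 92% v 80% power is 77%. The 95% CI half-width for 4 minus 3 under the planned rates is 1.96 × √(0.2875/120) = 9.6 points.

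**Contrast in 11.1.** With group 1 as reference, the group 4 coefficient is the log odds ratio of group 4 v 1. The 4 v 2 and 4 v 3 effects are differences between coefficients (β4 − β2 and β4 − β3), which the section does not define.

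**Enrolment.** 480/0.80 = 600, which leaves 620 − 600 = 20 places (3.2%) for screen failures.

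**The case against.** Four points on the other side have force.

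- A reader might infer that the combination question is nearly certain to end inconclusive. The documents do not support that. The comparison with SGR alone has power above 99.9%, and the chance of a non-significant 4 v 3 result is 83–86%: very likely, not nearly certain. Moreover, if 11.1 is followed literally, the group 4 coefficient tests 4 v 1 with power near 100%. The likelier outcome is then a significant result mislabelled as benefit over single therapy.
- The 14–17% might be taken as the power of Hypothesis 3 as a whole. It applies only to the 2-mile run. Hypothesis 3 also covers time to and duration of return to duty, and section 10.2 lists several scales among the primary outcomes. No rates or variances are given for these, so their power is unknown.
- Section 11.5 names no link, and a probit interaction test does reach about 81% at 380, so it cannot be said that no reading yields 80%. But 11.1 specifies logistic regression, and on either scale the interaction has the wrong sign for the claim. That the 380 came from such a test is only an inference.
- No section says that a null 4 v 3 result will be read as SGR being unnecessary. Section 9.3 states an aim, not a decision rule. The risk of misreading is real, but it is not the plan's stated intention.

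It is also tempting to say that 11.4 and 11.5 contradict each other on the 620. They need not: both figures are ceilings, and attrition is only approximate. The margin for screen failures is thin and the meaning of 620 is unclear, which calls for a clarification and no more.

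None of this alters the core result: the stated 80% is wrong for the comparison that 11.5 names.

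**Conclusion.** The power statement needs correcting. On the plan's own 2-mile-run rates, equal allocation and a two-sided 0.05 test, combined therapy v BoNT-A with home-based retraining has about 14% power at 380, 17% at 480 and 21% at 620, against the stated 80%. Power to beat both single therapies on this endpoint is also about 14–17% at 380–480, and superiority over BoNT-A with home-based retraining will most likely not be shown. The comparison with SGR alone is amply powered. The result does not depend on sidedness. It does depend on the assumed 80% and 85%: a larger true gap would raise the power, but the plan assumes none.

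**What to change.** No patients need be added.

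1. In 11.5, replace the single 80% figure with separate power on the 2-mile run: above 99.9% for group 4 v 2, and 14% at 380 and 17% at 480 for group 4 v 3. State the sidedness and the contrast used, and give the detectable rate (about 92.5% v 80% at 120 per arm).
2. In 11.1, define aim 3 as two explicit contrasts, group 4 minus group 2 and group 4 minus group 3, and remove the statement that the group 4 coefficient estimates them.
3. Commit to reporting the 4 minus 3 difference with its 95% CI (expected half-width about 9.6 points at 120 per arm). State there and in 9.3 that a non-significant result is not evidence that SGR is unnecessary.
4. As a secondary clarification in 11.2–11.5, say whether 620 counts consented or randomised participants.

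The cost is a text amendment and a less favourable stated power for the combination question.

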12.0 Participant Information

12.1 Subject Population:

Active duty service members aged 18-60 (inclusive) diagnosed with Chronic Exertional Compartment Syndrome (CECS) of their anterior and/or lateral compartments in their lower leg.

12.2 Age Range:

Check all the boxes that apply. If the age range of potential subjects (specimens, records) does not match the range(s) selected, please specify in the text box.

- ☐ 0-17
- ☒ 18-24
- ☒ 25-34
- ☒ 35-44
- ☒ 45-54
- ☒ 55-64
- ☐ 65-74
- ☐ 75+

18-60 (inclusive)

12.3 Gender:

- ☒ Male
- ☒ Female
- ☐ Other

12.4 Special categories, check all that apply

- ☐ Minors /Children
- ☐ Students
- ☐ Employees - Civilian
- ☐ Employees - Contractor
- ☐ Resident/trainee
- ☐ Cadets /Midshipmen
- ☒ Active Duty Military Personnel
- ☐ Wounded Warriors
- ☐ Economically Disadvantaged Persons
- ☐ Educationally Disadvantaged Persons
- ☐ Physically Challenged (Physical challenges include visual and/or auditory impairment)
- ☐ Persons with Impaired Decisional Capacity
- ☐ Prisoners
- ☐ Pregnant Women, Fetuses, and Neonates
- ☐ Non-English Speakers
- ☐ International Research involving Foreign Nationals - Headquarters Review is necessary

You must also consider the requirements of DoDI 3216.02, Enclosure 3, paragraph 7.e.

12.5 Inclusion Criteria:

Order Number	Criteria
1	Active duty service member age 18-60 (inclusive).
2	Fluent in speaking and reading English
3	Unable to run 2 miles without producing pain and/or symptoms, including aching, burning, numbness, tingling, and/or weakness in the affected limb.
4	Has difficulty completing the running portion of their service specific physical training due to pain and/or symptoms in the affected limb.

5	Meets clinical diagnostic criteria for CECS of the anterior and/or lateral compartment(s) in the lower leg, per clinical exams (e.g., physical examination, intramuscular compartment pressure test (IMCP test needle testing), lower leg MRI, etc.).
---	---

12.6 Exclusion Criteria:

Order Number	Criteria
1	Prior Botulinum toxin injection(s) in the lower leg compartments of the affected limb.
2	Prior compartment release of the affected limb.
3	Recent (within the last 6 months) lower limb injury that needed medical intervention
4	Undergone formal gait retraining within the last 6 months.
5	Allergic to BoNT-A (trade names BOTOX® or Xeomin®)
6	Pregnant or breastfeeding.
7	Medical history and/or clinical exams (e.g., physical examination, intramuscular compartment pressure test, lower limb MRI, amyotrophic lateral sclerosis (ALS), myasthenia gravis, Lambert-Eaton Syndrome, or any neuromuscular junction disorders) indicate other more likely causes of leg pain and/or symptoms.
8	Ankle Brachial Index (ABI) blood pressure ≤ 0.90 or ≥ 1.4 within the last 6 months. Post Exertion ABI is >0.2 or limb pressure decreases > 30 mmHg.

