If a potential participant expresses interest in learning more about the research study, a member of the research staff will briefly introduce the study, express the voluntary nature of participation, assess interest in participating, and screen the potential participant for initial eligibility in close collaboration with the patient's attending provider. Initial eligibility (see Section 12.5 Inclusion Criteria #1-5 & Section 12.6 Exclusion Criteria #1-8) will be confirmed using an Inclusion/Exclusion CRF (Appendix A). This Inclusion/Exclusion CRF does not record any PII/PHI.

If the potential participant meets initial eligibility criteria as determined by the Inclusion/Exclusion CRF and expresses interest in participating, an authorized study team member will initiate the formal consent discussion and, if applicable, obtain informed consent.

If a potential participant would like additional time to review the consent form, study procedures, risks and benefits, etc. they will be provided with a consent form and study brochure to take home and, if applicable, they may return to clinic at a later date to have any and all remaining questions answered and to finish the consent process.

Following completion of informed consent, the results of the Inclusion/Exclusion CRF will be entered into REDCap, an encrypted, access controlled, password protected electronic data capture and management system housed on a DoD server and maintained by the Uniformed Services University Information Technology (USU IT), by an authorized local study team member and a unique study ID will be automatically generated. This coded study ID will be used on all research data collection forms in place of the participant's name, social security number, Department of Defense (DoD) ID, or other protected identifier. No PII will be entered into REDCap. Please see Appendix J for additional information on REDCap.

In order to document screen failures and refusals, the results of the Inclusion/Exclusion CRF will be entered into REDCap even if a patient doesn't consent to participate in the study. The Inclusion/Exclusion CRF does not record any PHI/PII.

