offending exertional activity, they will then have repeat IMCP test done at 1 minute post exertion. The IMCP test is currently the diagnostic standard for CECS. The use of ultrasound imaging will be used to identify and mark the region of interest of the anterior and lateral leg compartments that will be tested. If a participant has had any of these procedures performed within the 6 months prior to study enrollment, the research team will review those results and not repeat procedures if the testing was adequate and acceptable for clinical standards.

Also as part of the formal screening procedures, participants will have their ankle brachial index (ABI) blood pressure taken on each side at their ankle, foot, and arm separately using a blood pressure cuff and Doppler instrument. Blood pressures will be taken at rest, then 1 minute within completing approximately 50 repetitions of bilateral heel raises. At rest, an ABI measurement of less than or equal to 0.90 or greater than or equal to 1.4 on either side will be excluded from the study and resume normal care with their referring provider. If their ABI post exertion decreases in value greater than 0.2 compared to baseline, limb pressures are decreased greater than 30 mmHg compared to baseline, or they meet the previous exclusion baseline criteria for their ABI, then the participant will be excluded from the study and resume normal care with their referring provider.

Any female participant will also be required to have a urine hCG test performed prior to study injection. If the urine hCG indicates the participant is pregnant, per stated inclusion/exclusion criteria, they will be formally withdrawn from the study and will resume normal care with their referring provider.

All of the formal screening procedures must be completed within 60 days post-study consent.

Demographics & Baseline Data Collection:

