Participants who meet final eligibility criteria (no other concomitant causes of leg pain, confirmed CECS diagnosis of the anterior and/or lateral compartments via intramuscular compartment pressure test and lower limb MRI, ABI between 0.90 and 1.40, and if applicable, negative pregnancy test) will be randomized to a study arm and their intervention dates (i.e. injection and/or supervised gait retraining) will be scheduled. Study injections (both placebo and BoNT-A) must occur within 60 days of randomization and ≥ 2 weeks post-intramuscular compartment pressure test. A computer-generated randomization program prepared by the study biostatistician will be used to assign participants uniformly across all four study arms.

Participants will be assigned to one of four treatment groups:

- Group 1 - Home Based Gait Retraining (HBGR) and Normal Saline (placebo)
- Group 2 - Supervised Gait Retraining (SGR) and Normal Saline (placebo)
- Group 3 - BoNT-A + HBGR
- Group 4 - BoNT-A + SGR

Study Intervention:

BoNT-A Injections:

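### Exclusion 8 limits the post-exertion ABI itself, while 10.1 and 13.3 limit its fall from baseline; the ABI rule needs one wording

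*Combined protocol and SAP*

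**What the plan says.** The ABI rule appears in four places and in three versions.

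- **Sections 10.1 (Formal Screening) and 13.3, same wording.** At rest, the excluding condition is "At rest, an ABI measurement of less than or equal to 0.90 or greater than or equal to 1.4 on either side". After exertion there are three further grounds. The first concerns the change in the index: "If their ABI post exertion decreases in value greater than 0.2 compared to baseline". The second is a drop in limb pressure of more than 30 mmHg from its baseline value. The third brings back the resting limits: "or they meet the previous exclusion baseline criteria for their ABI".
- **Section 10.1 (Randomization).** The summary of final eligibility gives only "ABI between 0.90 and 1.40". It has no post-exertion condition and does not say whether the end points are included.
- **Section 12.6, exclusion 8.** It begins with "Ankle Brachial Index (ABI) blood pressure ≤ 0.90 or ≥ 1.4 within the last 6 months", which does not mention rest or side, and continues with "Post Exertion ABI is >0.2 or limb pressure decreases > 30 mmHg".

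On timing, the pre-consent part of 10.1 states that "Section 12.6 Exclusion Criteria #1-8) will be confirmed using an Inclusion/Exclusion CRF". The ABI measurement itself belongs to formal screening, which follows consent. Section 13.6 provides for removing participants who do not meet the screening criteria in 13.3.

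**The concern.** In exclusion 8 the verb for a fall is attached only to limb pressure. The 0.2 therefore reads as a limit on the post-exertion ABI, where 10.1 and 13.3 make it a limit on the change from baseline. These are different quantities, and the same number cannot sensibly serve for both when the resting ABI has to exceed 0.90.

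The numbered exclusions are an operative list: staff confirm them on a CRF, and the results go into the database even for people who fail screening or decline. A multi-site trial needs that list to say the same thing as the screening procedure. Otherwise each site must work out the intended rule for itself, and a screen failure recorded against exclusion 8 has no single meaning.

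**Working it through.** The plan states no figure on this point that could be reproduced. The check compares the sets of people each version admits. Write R for the resting ABI and P for the post-exertion ABI.

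**Conditions to pass, from the text**

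- 10.1/13.3: 0.90 < R < 1.4; R − P ≤ 0.2; 0.90 < P < 1.4 (the re-applied limits); limb-pressure fall ≤ 30 mmHg.
- 12.6 number 8, literal: 0.90 < ABI < 1.4, taken here as R; P ≤ 0.2; limb-pressure fall ≤ 30 mmHg.
- 10.1 Randomization: ABI between 0.90 and 1.40, taken here as R with both ends included; nothing on P.

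**Do 10.1/13.3 and literal exclusion 8 overlap?**

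- Under 10.1/13.3 the decrease rule alone gives P ≥ R − 0.2 > 0.90 − 0.2 = 0.70. With the re-applied limits, P > 0.90.
- Under literal exclusion 8, P ≤ 0.2, so R − P > 0.90 − 0.2 = 0.70. That is more than three times the fall that 10.1/13.3 allow.
- The two sets share no one, and no outside figure is needed to show it. On a grid in steps of 0.01, 10.1/13.3 admit 1,995 (R, P) pairs, and 0 of them pass literal exclusion 8.

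**Exclusion 8 on its own.** Its ABI part is not empty: R from 0.91 to 1.39 (49 values) and P from 0 to 0.20 (21 values) give 49 × 21 = 1,029 grid pairs. Its limb-pressure part then has to be added, which needs arm pressures that the documents do not give. Take limb pressure as ankle pressure, B as resting arm systolic pressure and r as the post/rest arm-pressure ratio. The ankle fall exceeds 0.90B − 0.2rB, so a fall within 30 mmHg needs B < 30/(0.9 − 0.2r). That is about 43, 46, 50 and 60 mmHg for r = 1, 1.25, 1.5 and 2. For an assumed B of 90 to 160 mmHg, the lower bound on the fall runs from 45 mmHg (B = 90, r = 2) to 112 mmHg (B = 160, r = 1). Exclusion 8 alone is therefore empty only under an assumption about arm pressure.

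**Worked cases** (limb pressure assumed not to fall by more than 30 mmHg)

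| R / P | Fall R − P | 10.1 and 13.3 | 12.6 no. 8, literal | 10.1 Randomization |
|---|---|---|---|---|
| 1.10 / 1.05 | 0.05 | passes | excluded | passes |
| 1.25 / 1.00 | 0.25 | excluded | excluded | passes |
| 1.35 / 1.42 | −0.07 (a rise) | excluded, P ≥ 1.4 | excluded | passes |
| 0.90 / 0.90 | 0 | excluded | excluded | passes |
| 1.40 / 1.30 | 0.10 | excluded | excluded | passes |

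**If exclusion 8 is read as a fall of more than 0.2.** The first case then passes and the second stays excluded, in line with 10.1/13.3. The third case remains unclear. Exclusion 8 does not re-apply the limits after exertion, yet its first sentence does not confine them to rest either. The last two cases turn on whether the Randomization sentence includes its end points.

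**Look-back and timing.** Sections 10.1 and 13.3 let staff reuse test results from the 6 months before enrolment, but that sentence stands before the ABI paragraph and does not clearly cover it. Exclusion 8 carries its own 6-month look-back. If no earlier ABI exists, the criterion cannot be confirmed before consent, because the measurement has not yet been made.

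**The case against.** The strongest reply is that this is a visible slip with no effect on conduct. The text at the point of measurement is clear and is given twice in the same words, and section 13.6 makes the 13.3 criteria the ground for removal. Exclusion 8 can be read in their light, since its next clause speaks of a decrease. A rule that turned everyone away would be noticed at first use. The Randomization sentence summarises people who have already passed formal screening, so its silence on exertion admits no one new if the steps are followed in order.

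Most of this stands. A dropped word is the likely cause, and the Randomization sentence is incomplete rather than a rival route into the trial. Two things remain. The numbered list is checked in its own right, and the protocol does not rank it below 13.3. Reading exclusion 8 charitably also leaves the end points, the re-applied limits, the look-back and the timing unsettled.

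A reader might infer that the trial can enrol nobody, or 0 of 620. The documents do not support that. The empty set comes from combining exclusion 8 with 10.1, 620 is an enrolment ceiling (11.2, 11.3) and not a count of people screened, and 13.3 governs removal. A reader might also infer that the randomised population has shifted or that protocol-deviation counts are void. Nothing in the documents shows either.

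**Conclusion.** Exclusion 8 is wrong as written. Its post-exertion condition contradicts 10.1 and 13.3, and taken literally it excludes every person those sections admit. That result needs only the limits printed in the protocol. The further differences between the versions are real but smaller.

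The finding concerns the consistency of the eligibility text. It does not touch the sample size, power, error rate or analysis, and no number of affected participants can be given. Whether the error reaches sites in practice depends on the Inclusion/Exclusion CRF (Appendix A), which is not among the documents supplied. Which threshold is clinically right is not judged here.

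**What to change.** Reconcile the four places (10.1 Formal Screening, 10.1 Randomization, 12.6 number 8 and 13.3) into one ABI rule, worded identically in each. The rule should settle:

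- whether the 0.2 refers to a change or to an absolute value;
- whether the resting limits include their end points, and that they apply to either side;
- whether those limits apply again after exertion;
- the limb-pressure condition and its reference value;
- whether an ABI from the previous 6 months may be used;
- whether the check is made before consent, after it, or in two stated steps.

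The sponsor's clinicians should confirm the thresholds. The Inclusion/Exclusion CRF should then be compared with the agreed text and corrected if it differs. The cost is a wording amendment and a CRF check, with no new measurement and no change to the design or analysis.
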